9.2. Setting

This study will be conducted using Optum's COVID-19 Electronic Health Record Data during the period of January 01, 2020, to June 30, 2024. Details about the database are found in Section 9.6. The COVID-era cohorts will be refreshed annually to include additional individuals, follow-up time, and events. These refreshes and cohorts will accordingly be described in a Statistical Analysis Plan (SAP) or protocol amendment as appropriate.

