9.2.2.4. Follow-up

The follow-up period starts at index date and participants will be followed until the date of the first occurring of the following events:

- Death;
- At the end of their database disenrollment from the database;
- At the end of study period (Section 9.2.2.1);
- Occurrence of the outcome of interest.

Follow-up time for hospitalized patients will meet the criterion in Section 9.2.1 (ie, hospitalized within 30 days of COVID 19 diagnosis or index date). Details as well as follow-up windows for long COVID will be defined in SAP.

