9.4. Variables

Outcome events will be the pre-specified potential safety concerns, including those that were part of Paxlovid or identified after the EUA post marketing. The list of events of interest is provided below. This list of outcome events was chosen based on clinician's expert opinion, biologic plausibility, and feasibility of identification in EHR or claims data. Other potential safety concerns that arise during the post marketing, clinical trials, or based on emerging literature related to Paxlovid safety will be included in subsequent refreshes of the cohorts, or as rapid queries in response to regulatory authority requests.

Potential Safety Outcomes of Interests*

- 1. Renal impairment.
- Hepatic impairment.
- 3. Other potential safety events of interest (eg, Diarrhea, Dysgeusia, Hypersensitivity reaction/allergic reactions, and other additional potential safety events of interest may be added over time).

* The potential safety outcomes of interests listed above can be further evaluated by the covariates including (demongraphics, drug-drug interactions etc.).

Potential effectiveness of interests*

- Hospitalization;
- All-cause mortality;
- ICU/Mechanical Vitalization;
- In Hospital death.

COVID-19 complications/interventions (within 30 days of COVID 19 diagnosis):

- Pneumonia;
- Kidney failure;
- Thrombotic event;
- Acute respiratory distress syndrome (ARDS);
- HF;
- Sepsis/septic shock;
- Hospitalization;
- All-cause mortality;
- In hospital death;
- Multi-organ dysfunction/failure;
- Mechanical ventilation/ECMO (Extracorporeal membrane oxygenation).
- Vasopressor use

Time to clinical events:

- Time from index date (Section 9.2.2.3) to admission;
- Time from index date (Section 9.2.2.3) to the events above.

^{*}The outcomes may be removed to added depending on the data availability for proper analyses.

COVID-19 long term health effects:

Headache;

The following conditions may be considered for COVID-19 long term effects. This is not an exclusive list. Specific definition and follow up windows of long COVID (eg, greater than 4 weeks, 12 weeks, or 6 months after a COVID diagnosis)⁹⁻¹⁰ will be further defined in SAP.

4 weeks, 12 weeks, or 6 months after a COVID diagnosis) ⁹⁻¹⁰ will be further defined in SAP.
Abdominal pain;
Acute kidney injury;
Alopecia;
Body aches;
• Chest pain;
Cognitive impairment;
• Confusion/delirium;
Nasal congestion;
• Cough;
Anxiety disorders;

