9.9. Data Analysis

Baseline characteristics will be summarized for Source Cohort, Trial Similar Subcohorts, and Paxlovid cohort. Means with standard deviations, medians with interquartile will be provided for continuous variables. Numbers and percentages will be provided for dichotomous variables or categorical variables.

For dichotomous endpoints such as COVID-19 complications and outcomes, the crude cumulative incidence and incidence rate of each endpoint will be estimated for the Source Cohort and the Trial Similar Subcohorts. For incidence calculation, only the first of each event occurring in the risk window will be included in the numerator. How to handle prevalence cases prior to the index date for incidence calculation will be further described in SAP depending on the nature of outcomes (eg, acute vs. chronic evets). Cumulative incidence and its 95% confidence interval (CI) will be estimated and illustrated using 1-Kaplan-Meier curves. Incidence rate will be calculated as the number of patients who experience the event divided by the total person time at risk, along with the 95% CI. The follow-up will start on the index date and will end on the first occurrence of an endpoint, disenrollment, study end date, or death, whichever comes first. Different endpoints will not censor each other's follow-up. Subpopulation analyses, as needed, will be detailed in SAP that may include those immunocompromised patients, pediatric population, severe renal patients, Paxlovid users with contraindication medications, patients with multiple infections of COVID 19, or patients received COVID 19 vaccines etc.

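### For the 30-day COVID-19 complications, the listed ends of follow-up omit day 30, so the incidence rate, read literally, divides 30-day events by person-time running on to study end

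*Protocol*

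**What the plan says.** Protocol 9.4 lists twelve outcomes, from pneumonia and ARDS to hospitalization and all-cause mortality, under the heading "COVID-19 complications/interventions (within 30 days of COVID 19 diagnosis". For incidence, 9.9 states that "only the first of each event occurring in the risk window will be included in the numerator" and defines the rate as "the number of patients who experience the event divided by the total person time at risk".

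The next sentence of 9.9 fixes the person-time: "The follow-up will start on the index date and will end on the first occurrence of an endpoint, disenrollment, study end date, or death", whichever is earliest. Section 9.2.2.4 says that "participants will be followed until the date of the first occurring of the following events" and lists death, disenrollment, "At the end of study period (Section 9.2.2.1") and the outcome itself. Neither list has an end at day 30.

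The data span is "during the period of January 01, 2020, to June 30, 2024" (9.2), with annual refreshes that add follow-up time. Section 9.2.2.4 leaves some matters open: "Details as well as follow-up windows for long COVID will be defined in SAP". The companion measure in 9.9 is cumulative incidence from 1-Kaplan-Meier curves.

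**The concern.** A rate is interpretable only if numerator and denominator cover the same days. Here the numerator closes at day 30. Under the listed ends, the denominator stays open for every event-free patient until disenrollment, death or study end, possibly for years. The result then reflects mainly how long the database observes people, not how often complications occur.

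The incidence rate is one of two measures planned for these endpoints and serves primary Objective 3, on background incidence. Section 7 wants such rates as context for events seen in trials and after marketing. A background rate that is too low makes an observed rate look excessive. Results are also stratified by calendar period (9.2.2.1) and refreshed, so figures resting on very different follow-up will be seen side by side.

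**Working it through.** The protocol states no expected rate, risk or event count, so there is no figure of its own to reproduce. The check shows what the literal rule does to a known risk.

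**Inputs from the protocol.** Window 30 days (9.4); data from 1 January 2020 to 30 June 2024 (9.2); T1 from 1 January to 31 October 2020; T4 from 22 December 2021 (9.2.2.1).

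**Assumptions.** 30-day risk r = 5%; events on average at day 5; index dates uniform within each period; follow-up to 30 June 2024; no disenrollment.

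**Mean follow-up of event-free patients (F).**
- All index dates: 1,642 / 2 = 821 days.
- T1: (1,642 + 1,338) / 2 = 1,490 days.
- T4: 921 / 2 = 460.5 days.

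**Formula.** Rate per 100 person-years = 100 × r × 365.25 / [(1 − r) × F + r × 5] = 1,826.25 / (0.95 × F + 0.25).

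| Person-time | F (days) | Denominator | Rate per 100 PY | Understated by |
|---|---|---|---|---|
| Ended at day 30 | 30 | 28.75 | 63.5 | – |
| Short follow-up (assumed) | 180 | 171.25 | 10.7 | 6.0-fold |
| T4 to June 2024 | 460.5 | 437.73 | 4.2 | 15-fold |
| All to June 2024 | 821 | 780.20 | 2.3 | 27-fold |
| T1 to June 2024 | 1,490 | 1,415.75 | 1.3 | 49-fold |

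**Sensitivity.** A second calculation used a constant hazard over days 0 to 30. Person-time ended at day 30 gives 62.4 at 5% risk, whatever the period or data cut.
- *Risk level.* At 1,490 days the understatement is 49-, 48- and 47-fold for risks of 1%, 5% and 10%, so it hardly depends on the risk.
- *Disenrollment.* At 20% a year, 48-fold at 1,490 days becomes 33-fold, and 15-fold at 461 days becomes 13-fold.
- *Late index dates.* Patients indexed in the last 30 days of data are unaffected.

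**Between periods, same true risk (constant hazard).**
- T1 followed to June 2024: T1 1.29, T4 4.10, so T4 appears 3.2 times T1 (2.6 times at 20% yearly disenrollment, 2.0 at 50%).
- T1 followed only to 31 October 2020: T1 about 12.0 against T4 4.10, so the order reverses.

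**Between data cuts (constant hazard, no disenrollment).**
- One index date, 15 January 2022, at the June 2022, 2023 and 2024 cuts (166, 531 and 897 days): 11.5, 3.6, 2.1.
- Open cohort, uniform accrual, same cuts: 4.14, 2.97, 2.32.
- Open cohort with an assumed 5-fold accrual surge from 20 December 2021 to 30 June 2022: 6.82, 6.29, 3.33, 2.32 at the June cuts of 2021 to 2024, but a rise from 5.60 to 6.29 between 31 January and 30 June 2022.

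**Kaplan-Meier.** An event-free patient observed beyond day 30 leaves the curve up to day 30 unchanged, so cumulative incidence read there is not distorted.

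**The case against.** The best defence is that 9.9 divides by time at risk, not by all follow-up, shortly after introducing a risk window. On that view, time at risk means time inside the window, and the follow-up sentence only sets general limits for all endpoints. This is a fair reading. But the follow-up sentence comes straight after the rate definition, gives its ends as whichever comes first, and leaves the window out. The passage therefore at best conflicts with itself.

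It can also be said that endpoint windows belong in the SAP, which is not at hand and may already end person-time at day 30. How the rates will actually be computed is therefore unknown. Still, the deferral of windows in 9.2.2.4 is tied to long COVID, whereas the 30-day window and the ends of follow-up are fixed in the protocol. The point concerns a stated rule, not missing detail.

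Three stronger inferences are tempting, and the documents do not support them:

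- *Early periods are always diluted most, so T4 will look about three times T1.* This needs T1 patients to be followed to study end. Section 9.2.2.4 ends follow-up at the study period of 9.2.2.1, which also labels T1 to T4 as study periods. If T1 closes on 31 October 2020, the direction reverses. No formal comparison is planned either: 9.7 calls the study descriptive and puts comparative analyses out of scope.
- *The rate falls at every refresh.* This holds for a closed period whose patients remain under observation. In an open cohort it is usual but not certain, as the surge example shows.
- *All the incidence results are wrong.* Only the person-time rate for the 30-day endpoints is affected. Objective 3 can still be answered from cumulative incidence. Hospitalization and all-cause mortality also appear in 9.4 as effectiveness outcomes without a 30-day window, and those versions are untouched.

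**Conclusion.** The point holds for the person-time incidence rate of the complications and interventions that 9.4 limits to 30 days. Followed literally, 9.2.2.4 and 9.9 add person-time in which no event can count. At best the text is open to two readings that give very different rates.

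The understatement is about 6-fold at 180 days' mean follow-up and about 15- to 50-fold at 460 to 1,490 days without disenrollment. It is smaller with disenrollment and nil for patients indexed in the last 30 days. All these multipliers rest on assumed follow-up, because the protocol gives no follow-up or disenrollment figures. Under the literal rule the rate can only be too low, whatever the assumptions.

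Rates would not be comparable across periods or data cuts with different follow-up. The documents do not settle which of T1 and T4 would look higher.

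**What to change.** In 9.2.2.4 and 9.9, add to the events ending follow-up for these endpoints: end of the endpoint's risk window (day 30 for the COVID-19 complications/interventions in 9.4). State that the already planned cumulative incidence for them is read at day 30. Leave the rule unchanged for endpoints without a 30-day window.

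The cost is one sentence in the protocol, matched in the SAP, and one more date in the calculation of follow-up end. No new data are needed. If the SAP already ends person-time at day 30, the change only brings the protocol into line.

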9.2.1. Study Population and Cohorts

The study population will consist of patients who tested positive or were diagnosed for COVID-19 (ie, positive PCR or antigen results of direct SARS-CoV-2 viral testing or have confirmed COVID-19 diagnosis codes). All Paxlovid users will be included in the study.

Within the study population, three source cohorts of general population with COVID-19 will be formed (Figure 1):

- 1a: Overall COVID-19 patients.
- 1b: Hospitalized patients (ie, hospitalized within 30 days of index date) for COVID-19
- 1c: Non-hospitalized patients (ie, not hospitalized within 30 days of index date) with COVID-19

Within source cohort of 1a, 1b, and 1c, the following trial similar subcohorts, will be formed:

Patients at high risk of progression to severe illness (Figure 1)

- 2a: Subgroup of the general population cohort 1a who meet relevant inclusion/exclusion criteria of the Paxlovid clinical trial (C4671005).
- 2b: Subgroup of the hospitalized patient cohort 1b who meet relevant inclusion/exclusion criteria of the Paxlovid clinical trial (C4671005).
- 2c: Subgroup of the non-hospitalized patient cohort 1c who meet relevant inclusion/exclusion criteria of the Paxlovid clinical trial (C4671005).

Patients at standard risk of progression to severe illness Figure 1)

- 3a: Subgroup of the general population cohort 1a who meet relevant inclusion/exclusion criteria of the Paxlovid clinical trial (C4671002).
- 3b: Subgroup of the hospitalized patient cohort 1b who meet relevant inclusion/exclusion criteria of the Paxlovid clinical trial (C4671002).

[figure not shown]
 3c: Subgroup of the non-hospitalized patient cohort 1c who meet relevant inclusion/exclusion criteria of the Paxlovid clinical trial (C4671002).

A sub-cohort of patients who were exposed to Paxlovid in real world settings will be created.

If a patient had an exposure to paxlovid without COVID PCR/antigen testing/diagnosis data, this patient can be captured in the Paxlovid cohort.

Additional special populations (eg, immunocompromised patients, pediatric population, severe renal impairment, etc.) may be added as a subset.

A validation substudy will be a subpopulation randomly drawn from within the OPTUM EHR database. Figure 1. Flowchart Outlining the Study Cohort and Subcohorts

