9.7. Study Size

This is a descriptive study with no minimum sample size. This study will be updated with new data annually (or as needed) and made readily accessible to address research questions. All eligible patients during the relevant study periods will be included. If there is a need to add on post-hoc comparative studies analyses, which are not part of the scope of this current study, the feasibility of robust comparisons given accrued sample size will be assessed as described in the SAP.

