For exploratory analysis, machine learning models (eg, LASSO Cox regression, Random Survival Forest (RSF), and XGBoosting (XGB) models) will be used to identify important predictors associated with progression to COVID-19 severe outcomes/manifestations as well as long COIVD. An ensemble method will be used to rank predictors across models and find the strongest predictors for each outcome. Patient-level prediction for the risk of developing severe outcomes/manifestation and long COVID will be performed using the top ensemble predictors. C-index and dynamic AUCs will be used to evaluate model performance. To assess the feasibility of real-world effectiveness of Paxlovid, we will apply propensity score matching (PSM) method to control confounding and PTDM to handle immortal bias. To better understand the impact of incidental hospitalization on the same date of COVID 19 diagnosis date or Paxlovid prescription date, medical note review of patients with the same date hospitalization will be conducted by OPTUM. The structured data (Hospitalization on the same date = Yes/No) will be provided by OPTUM to enable the assessment of misclassification of the hospitalization.

All data analysis will be executed using statistical software SAS version 9.4 or later.

Detailed methodology for statistical analyses in this study will be documented in a statistical analysis plan (SAP), which will be dated, filed, and maintained. The SAP may modify the plans outlined in the protocol; any major modifications of primary endpoint definitions or their analyses would be reflected in a protocol amendment.

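### The note review in section 9.9 aims at incidental hospitalization, but the only field it names repeats the selection criterion and does not record why the patient was admitted

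*Protocol*

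**What the plan says.** Protocol section 9.9 gives the purpose of the review: "To better understand the impact of incidental hospitalization on the same date of COVID 19 diagnosis date or Paxlovid prescription date". It then names who is reviewed and by whom: "medical note review of patients with the same date hospitalization will be conducted by OPTUM". The next sentence names the output: "The structured data (Hospitalization on the same date = Yes/No) will be provided by OPTUM to enable the assessment of misclassification of the hospitalization". No other returned variable is mentioned.

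Three other places bear on what hospitalization means in this study:

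- Section 9.2.1 defines a source cohort as "1b: Hospitalized patients (ie, hospitalized within 30 days of index date) for COVID-19". The label refers to a cause, while the definition refers only to timing.
- Section 9.4 lists hospitalization under "COVID-19 complications/interventions (within 30 days of COVID 19 diagnosis"), again by window and without a reason for admission. The same section lists it as a potential effectiveness outcome and lists time from index date to admission.
- Section 9.2.1 also mentions further validation in one sentence: "A validation substudy will be a subpopulation randomly drawn from within the OPTUM EHR database". It names no variables.

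**The concern.** Whether an admission is incidental depends on why the patient was admitted. The named field records whether there was an admission on a given date. The patients sent for review are there because the record already shows such an admission, so the field asks the notes to confirm what put the patient on the list.

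This matters because hospitalization has several roles. It is a complication, a potential effectiveness outcome and a time-to-event endpoint, and it separates cohorts 1b from 1c, 2b from 2c and 3b from 3c. Follow-up starts on the index date (sections 9.2.2.4 and 9.9), so same-date admissions fall at time zero. That is where an admission for another reason, with a positive test found on arrival, is most plausible. The sponsor saw the problem and planned a check. If the check is carried out as written, good agreement on admission dates could be read as reassurance about misclassification while the incidental share stays unmeasured.

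**Working it through.** The plan gives no figure to reproduce: section 9.7 states "This is a descriptive study with no minimum sample size", and no incidental share or same-date fraction appears anywhere. The main check is therefore one of logic, followed by an illustration of size.

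**Step 1: what the field can identify.** Let S be a same-date admission in the structured record, R the value returned from the notes (same-date admission, yes or no), and p the share of reviewed admissions that are incidental. Review is restricted to S = yes. Let c1 be the probability that the notes confirm the admission and date when it was for COVID-19, and c0 the same probability when it was incidental. Then

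P(R = yes | S = yes) = (1 − p) × c1 + p × c0.

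- If the notes always agree with the record (c1 = c0 = 1), the result is 100% yes for p = 0%, for p = 100% and for every value between.
- If confirmation is imperfect but unrelated to the reason (c1 = c0 = c), the result is c, and p drops out.
- If c1 and c0 differ, there is one observed proportion and three unknowns, so p still cannot be recovered.

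The review does yield P(R = no | S = yes), the proportion of recorded same-date admissions that the notes do not confirm. This is 1 minus the positive predictive value of the record for the fact or date of admission. Sensitivity cannot be estimated, because patients with S = no are not reviewed.

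**Step 2: whether another step supplies the reason.**

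- Section 9.2.1: cohort 1b is set by the 30-day window, and the validation substudy has no stated content.
- Section 9.3.2.1: the trial-similar exclusion concerns hospitalization in the 30 days before index and does not address why a same-date admission occurred.
- Section 9.4: hospitalization is listed without attribution.
- Section 9.5: the covariates and utilization variables include the number of hospitalizations and length of stay, but no reason for admission.
- Section 9.11: linked claims may be used to add patients or records, with no mention of reason for admission.

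None of these records it.

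**Step 3: illustration of size, with p assumed.** Among same-date admissions, counting all of them as COVID-attributable overstates the true number by 1/(1 − p):

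- p = 10%: 1/0.90 = 1.11
- p = 25%: 1/0.75 = 1.33
- p = 40%: 1/0.60 = 1.67

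For hospitalization within 30 days, let f be the fraction of admissions that are same-date, and suppose all later admissions are COVID-attributable. The factor is then 1/(1 − f × p). With f = 50%, also an assumption:

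- p = 10%: 1/(1 − 0.05) = 1.05
- p = 25%: 1/(1 − 0.125) = 1.14
- p = 40%: 1/(1 − 0.20) = 1.25

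The first set of factors is the limit f = 100%.

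**The case against.** The strongest reply is that the parenthesis may be shorthand. The preceding sentence states the aim, and a flag set after a note review directed at incidental admission could be meant as the adjudicated result, delivered in structured form because the sponsor works with structured, anonymized data. Section 9.9 does not say that nothing else is returned, and it leaves detailed methods to an SAP that is not shown. This stands as a reason for caution about intent. It does not remove the point: the protocol itself names a field, the field does not fit the aim, and an abstraction form built from the text would follow the text. An analysis plan cannot recover what was never abstracted.

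Four stronger readings are tempting, and the documents do not support them:

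- A reader might infer that the review is empty, with near-perfect agreement guaranteed. That depends on recorded admission dates being accurate, for which no figure is given. A no from the notes would reveal an unconfirmed or misdated admission, which is real misclassification of another kind.
- A reader might infer that this is the only validity check in the study. The validation substudy and the possible claims linkage are mentioned without enough content to rule that in or out.
- A reader might infer that incidental admissions make the hospitalization endpoints wrong. Section 9.4 requires no attribution and cohort 1b is operationalized by timing, so under those definitions such an admission is counted correctly. What suffers is its interpretation as a COVID-19 event.
- A reader might carry the 1.11 to 1.67 range over to the 30-day endpoints. It applies to same-date admissions only.

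It is also fair that this is a supplementary check in a descriptive study, described among the exploratory analyses, and that no primary estimate is computed from the flag.

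**Conclusion.** The point holds in a limited form. As written, the review can confirm or refute a recorded same-date admission but cannot tell an admission for COVID-19 from an incidental one, which is what it was planned to do. No other step described in the protocol fills that gap. The conclusion rests on a literal reading of the single variable named. If a COVID-19-related flag was meant, a change of wording is still needed.

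The size of the effect is unknown. The factors above rest on assumed incidental shares. For 30-day hospitalization they also rest on an assumed same-date fraction and on all later admissions being COVID-attributable; on those terms the overstatement is smaller than for same-date admissions alone. This should be fixed, but it does not undermine the study's descriptive estimates as defined.

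**What to change.** In section 9.9, define the returned structured field as the reason for the same-date admission, with the categories COVID-19, other reason and undeterminable. Preferably add a second field for the order of events: admission before or after the positive test, diagnosis or Paxlovid prescription. Both come from the notes already being read. State that the result will feed a sensitivity analysis of hospitalization incidence and of 1b/1c membership in which other-reason admissions are reclassified. Abstraction criteria and details of that analysis can sit in the SAP.

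The cost is slightly more abstraction per note and some undeterminable answers, whose share should be reported. The same patients and notes serve. The change should be made before abstraction begins, because adding the reason afterwards would mean returning to the notes.
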